3.5.2 Clinical Laboratory Tests

Laboratory assessments comprise safety laboratory tests (hematology, clinical chemistry and urinalysis) and other laboratory tests.

Descriptive statistics will be provided for clinical laboratory test results (hematology, clinical chemistry and routine urinalysis) and changes from baseline. With the exception of the LOCF sensitivity analysis of BK viremia, missing values for any of the laboratory evaluations will not be imputed; that is, only observed case data will be used.

A shift table, presenting the 2-way frequency tabulation for baseline and the worst post-baseline value according to the NCI CTCAE grade, will be provided for clinical laboratory.

In addition, the number and percentage of patients with the following potentially clinically significant abnormal liver function tests will be summarized:

- Potential Hy's Law cases: ALT or AST $\geq 3 \times \text{ULN}$ and total bilirubin $\geq 2 \times \text{ULN}$ and Alkaline phosphatase (ALP) $< 2 \times \text{ULN}$.

Listings will be presented for all laboratory data and all test values outside the normal range will be flagged.

In addition, other laboratory tests, including pregnancy test, serology test, testing for HIV, HCV, HBV and CMV, and donor specific anti-HLA antibodies will be presented in by-patient listings.

3.5.3 *Vital Signs*

Descriptive statistics will be provided for vital signs (including blood pressures, pulse rate, respiratory rate, oximetry, and body temperature), body weights, and BMIs by treatment group at each scheduled visit. Changes from baseline will also be summarized.

All vital sign data will be listed by patient.

3.5.4 *Electrocardiograms*

ECG measurements include heart rate (bpm), measures PR (msec), QRS (msec), QT (msec), and QTc (msec) (corrected using Fridericia's and Bazett's methods). Descriptive statistics will be provided for the observed measurements and change from baseline.

All ECG parameters and the Investigator interpretation of findings including details of any abnormalities will be listed by patient.

3.5.5 *Physical Examinations*

All abnormal physical examination findings, including details of any abnormalities will be listed by patient.

3.6 Data Safety Monitoring Board

An independent Data Safety Monitoring Board (DSMB) will be convened for this study to routinely monitor patient safety and evaluate pre-specified interim analyses to stop the study or either arm early. The DSMB will receive summary reports of all unexpected SAEs. A DSMB charter, detailing all aspects of the DSMB's composition, scope of review, and procedures will be provided in a separate document. In addition, the DSMB will review safety data after the first 3 patients enrolled have received their 3rd dose.

An unblinded statistician will be assigned to the DSMB. This statistician will not be involved in any aspects of study conduct outside of the DSMB, and their role will be defined in the DSMB charter.

APPENDIX A: SCHEDULE OF ACTIVITIES**Table 2: Schedule of Activities in Period 1 (Weeks -2 to 12)**

At the discretion of the Investigator, and with the exception of Weeks 8 and 12 (which must be conducted at the site), study visits for patients who have undetectable BK plasma viral load at 2 or more consecutive assessments at least 2 weeks apart after 3 doses may be conducted by a Sponsor-approved home health vendor in conjunction with a Sponsor-approved telehealth provider. These visits may be conducted via video or telephone call.

| Study Week | Weeks -2 to -1 | Day 1 | Week 1 | Week 2 | Week 4 | Week 6 | Week 8 | Week 10 | Week 12 |
|---|-------------------|-------------------|--------|------------------|-------------------|--------|-------------------|---------|-------------------|
| Study Day | -14 to -1 | 1 ^[1] | 8 | 15 | 29 | 43 | 57 | 71 | 85 |
| Visit Window (Days) | NA | NA | ±2 | ±3 | ±3 | ±3 | ±3 | ±3 | ±3 |
| Study Procedures | | | | | | | | | |
| Informed consent ^[2] | X | | | | | | | | |
| I/E criteria | X | X | | | | | | | |
| Demographics | X | | | | | | | | |
| Medical history | X | | | | | | | | |
| Prior & concomitant medications | X | X | X | X | X | X | X | X | X |
| Adverse events ^[3] | X | X | X | X | X | X | X | X | X |
| Complete physical examination ^[4] | X | X | | | | | | | X |
| Targeted physical examination ^[4] | | | X | X | X | X | X | X | |
| Weight and height ^[5] | X | X | | | X | | X | | X |
| Vital signs ^[6] | X | X | X | X | X | X | X | X | X |
| 12-lead ECG ^[7] | X | X ^[7] | | X ^[7] | | | | | |
| Documentation of HLA typing ^[8] | X | | | | | | | | |
| Clinical labs ^[9] | X | X | | X | X | X | X | X | X |
| Testing for HIV, HCV, and HBV ^[22] | X | | | | | | | | |
| BKV plasma viral load ^[10,11] | X | X | | X | X | X | X | X | X |
| Urine for biomarker ^[12] | | X | | | X | | X | | X |
| AdV, CMV, JCV, HHV-6 plasma, and EBV viral load ^[10] | | X | | | X | | X | | X |
| Pregnancy test | X ^[13] | X ^[14] | | | X ^[14] | | X ^[14] | | X ^[14] |
| FSH ^[15] | X | | | | | | | | |
| Randomization ^[16] | | X | | | | | | | |
| Provide patient cards | | X | | | | | | | |
| Study treatment administration ^[17] | | X | X | X | X | X | X | X | X |

| Study Week | Weeks -2 to -1 | Day 1 | Week 1 | Week 2 | Week 4 | Week 6 | Week 8 | Week 10 | Week 12 |
|---|-------------------|------------------|--------|--------|--------|--------|--------|---------|---------|
| Study Day | -14 to -1 | 1 ^[1] | 8 | 15 | 29 | 43 | 57 | 71 | 85 |
| Visit Window (Days) | NA | NA | ±2 | ±3 | ±3 | ±3 | ±3 | ±3 | ±3 |
| Post infusion monitoring ^[18] | | X | X | X | X | X | X | X | X |
| Banked PBMCs for virus specific immunity ^[19] | X | | | X | X | X | X | | X |
| Blood for donor DNA ^[20] | | | | | X | | | | X |
| Kidney biopsy pathologic specimens for review (if clinically indicated) ^[23] | X | X | X | X | X | X | X | X | X |
| Donor-specific antibodies ^[24] | | X | | | | | | | X |

1. Unless noted otherwise, the Day 1 procedures must be performed within 96 hours of randomization and prior to study treatment administration.
2. Prior to conducting any study-related activities, written informed consent to participate in the study must be provided by the patient.
3. Adverse events will be monitored and documented from randomization through Week 24 in all patients.
4. Complete physical examinations require the patient to be at the site, and will include, at a minimum, assessments of the Cardiovascular, Respiratory, Gastrointestinal and Neurological systems. Targeted physical examinations or assessments will include careful skin examination for GVHD, and other aspects as clinically indicated.
5. Height and weight will be measured at screening; only weight will be measured at other specified later visits. For home visits, stated weight may be used.
6. Includes body temperature, blood pressure, heart rate, and respiration rate and will be measured after resting for 5 minutes. For visits with infusions, vital signs will be measured within 30 minutes prior to infusion, at the end of the infusion, and at 15, 30, 45, and 60 minutes after the end of the infusion. A ±5 minute window will be permitted for all vital sign assessments.
7. Performed within 1 hour after study treatment administration and at the end of study or early termination visit. ECGs will be obtained with the patient in a semi-supine position after a 5-minute rest.
8. The HLA type of the patient and their donor kidney will be obtained from the medical record.
9. CBC must include differential and LFTs must include alkaline phosphatase, bilirubin, AST, and ALT. Urinalysis must be performed.
10. Viral loads of BKV in plasma will be measured. The results of analyses from screening must be available at the time of randomization. Results of central laboratory testing for viral load will be used for the purpose of determining eligibility/inclusion. Additional post-infusion samples may be collected, as clinically indicated. AdV, CMV, JCV, EBV, and HHV-6 viral loads will also be assessed. A whole blood or plasma BK viral load from the local laboratory may be used for the patient to qualify for screening if obtained ≤90 days before the start of screening and with any positive BK viral load (may be reported as either copies/mL or IU/mL).
11. Viral DNA isolated from blood samples will be stored for potential future sequencing/genotyping from the samples collected at baseline for viral load determination. Viral sequencing/genotyping will also potentially be performed in the event of viral recurrence and this sequencing result be compared with the baseline results.
12. Urine samples will be obtained and will be stored for urinary polyomavirus haufen testing.
13. A serum pregnancy test will be performed at screening for all patients of childbearing potential.
14. A urine pregnancy test will be performed at the site prior to study therapy initiation for patients of childbearing potential. If the result is negative, the patient will be eligible for study treatment administration and the remainder of the Day 1 testing/procedures will be performed. If the urine pregnancy result is positive, the patient must not receive study treatment. An on-site urine pregnancy test will also be performed at Weeks 4, 8, and 12 for patients of childbearing potential who are eligible for dosing. Dosing may only be completed following a negative test.

15. FSH will be tested at screening for women of nonchildbearing potential who are postmenopausal, defined as 12 consecutive months with no menses without an alternative medical cause.
16. Randomization will occur after all screening procedures are complete, after all eligibility criteria are met, and prior to study treatment administration. Randomization will mark the end of the screening period. Patients who meet all of the inclusion criteria and none of the exclusion criteria will be randomized to receive sequential infusions of PSL cells or placebo.
17. Patients will receive infusions of either PSL or placebo after all blood drawing procedures listed for their visit in the SoA. Patients in the active treatment arms will receive the same [REDACTED] dose for all infusions. Placebo infusions will be administered as appropriate to maintain the blind. As GVHD and CRS are a theoretical safety concern, the incidence and severity of GVHD and CRS will be monitored during the study. No patients are permitted to receive an infusion of PSL or placebo if they develop GVHD (\geq Stage 1; see Appendix 5, Section 10.5 of the protocol) or CRS >Grade 2. If any patient develops GVHD or CRS >Grade 2, study treatment infusions should be stopped immediately, and the patient treated per standard of care.
18. Patients will be monitored closely and must remain in the clinic for \leq 1 hour after the end of each infusion. Vital signs, including body temperature, heart rate, respiration rate, and blood pressure, will be measured within 30 minutes prior to infusion, at the end of the infusion, and at 15, 30, 45, and 60 minutes after the end of the infusion. A \pm 5 minute window is permitted for all vital sign measurements. Patients must also remain on continuous pulse oximetry for \leq 30 minutes after the end of the infusion. Post-infusion monitoring should be completed for all infusions of study treatment.
19. Blood will be collected into a cell separation tube and processed to generate a PBMC fraction and a plasma fraction. These fractions will be cryopreserved for potential future evaluation of virus-specific T cell immune function/virus-specific T cell persistence and for potential future evaluation of cytokines and/or other humoral markers of inflammation and/or immune function. In addition, a tube of whole blood will be collected for exploratory determination of virus-specific- T cell immune function in whole blood.
20. Blood will be obtained for (virus-specific T cell) donor DNA quantitation at Weeks 4, 12 and 24. Week 24 DNA may not be quantitated, depending on earlier results.
21. Week 24 procedures should be performed on any patient who terminates the study early before Week 24.
22. Serum will be screened for HIV, HBV and HCV antibodies with reflex nucleic acid testing of plasma.
23. Severity of Biopsy (for clinical indication) Proven Acute Rejection will be adjudicated by a blinded review via expert pathologists. No biopsies are required per the protocol.
24. Donor-specific antibody results should be derived from samples sent to the central laboratory.

Abbreviations: AdV = adenovirus; ALT = alanine aminotransferase; AST = aspartate aminotransferase; BKV = BK viremia; CBC = complete blood count; CMV = cytomegalovirus; CRS = cytokine release syndrome DNA = deoxyribonucleic acid; EBV = Epstein-Barr virus; ECG = electrocardiogram; ET = Early Termination Visit; FSH = follicle-stimulating hormone; GVHD = graft versus host disease; HBV = hepatitis B virus; HCV = hepatitis C virus; HIV = human immunodeficiency virus; HHV-6 = human herpesvirus 6; HLA = human leucocyte antigen; I/E = inclusion and exclusion; JCV = JC virus; LFT = liver function test; NA = not applicable; PBMC = peripheral blood mononuclear cell; PSL=psoluecel; SoA = Schedule of Activities

Table 3: Schedule of Activities in Period 2 (Weeks 14 to 24; Follow-Up Period)

At the discretion of the Investigator, all study visits during Period 2 may be conducted by a Sponsor-approved home health vendor in conjunction with a Sponsor-approved telehealth provider. These visits may be conducted via video or telephone call.

| Study Week | Week 14 | Week 16 | Week 18 | Week 20 | Week 22 | Week 24/ET ^[1] |
|---|---------|---------|---------|---------|---------|---------------------------|
| Study Day | 99 | 113 | 127 | 141 | 155 | 169 |
| Visit Window (Days) | ±7 Days |
| Study Procedures | | | | | | |
| Prior & concomitant medications | X | X | X | X | X | X |
| Adverse events ^[3] | X | X | X | X | X | X |
| Targeted physical examination ^[4] | X | X | X | X | X | X |
| Weight ^[5] | | X | | X | | X |
| Vital signs ^[6] | X | X | X | X | X | X |
| 12-lead ECG ^[7] | | | | | | X |
| Clinical labs ^[9] | | X | | X | | X |
| BKV plasma viral load ^[10,11] | X | X | X | X | X | X |
| AdV, CMV, JCV, EBV, and HHV-6 plasma viral load ^[10] | | X | | X | | X |
| Banked PBMCs for virus-specific immunity ^[19] | | X | | X | | X |
| Blood for donor DNA ^[20] | | | | | | X |
| Obtain any clinically indicated kidney biopsy pathologic specimens for review ^[23] | X | X | X | X | X | X |
| Donor-specific antibodies ^[24] | | | | | | X |

See footnotes and abbreviations following Table 3.

APPENDIX B: ANALYSIS VISIT WINDOWS

Table 1. Analysis Visit Windows for Physical Exams and Vital Signs

| Nominal Visit | Nominal Study Day | Visit Window Study Day | |
|----------------|-------------------|------------------------|-------------|
| | | Lower Limit | Upper Limit |
| Day 1/Baseline | 1 | 1 | 1 |
| Week 1 | 8 | 2 | 11 |
| Week 2 | 15 | 12 | 22 |
| Week 4 | 29 | 23 | 36 |
| Week 6 | 43 | 37 | 50 |
| Week 8 | 57 | 51 | 64 |
| Week 10 | 71 | 65 | 78 |
| Week 12 | 85 | 79 | 92 |
| Week 14 | 99 | 93 | 106 |
| Week 16 | 113 | 107 | 120 |
| Week 18 | 127 | 121 | 134 |
| Week 20 | 141 | 135 | 148 |
| Week 22 | 155 | 149 | 162 |
| Week 24 | 169 | >162 | |

Table 2. Analysis Visit Windows for BK Viral Loads

| Nominal Visit | Nominal Study Day | Visit Window Study Day | |
|----------------|-------------------|------------------------|-------------|
| | | Lower Limit | Upper Limit |
| Day 1/Baseline | 1 | 1 | 1 |
| Week 2 | 15 | 2 | 22 |
| Week 4 | 29 | 23 | 36 |
| Week 6 | 43 | 37 | 50 |
| Week 8 | 57 | 51 | 64 |
| Week 10 | 71 | 65 | 78 |
| Week 12 | 85 | 79 | 92 |

| | | | |
|---------|-----|------|-----|
| Week 14 | 99 | 93 | 106 |
| Week 16 | 113 | 107 | 120 |
| Week 18 | 127 | 121 | 134 |
| Week 20 | 141 | 135 | 148 |
| Week 22 | 155 | 149 | 162 |
| Week 24 | 169 | >162 | |

Table 3. Analysis Visit Windows for Clinical labs

| Nominal Visit | Nominal Study Day | Visit Window Study Day | |
|----------------|-------------------|------------------------|-------------|
| | | Lower Limit | Upper Limit |
| Day 1/Baseline | 1 | 1 | 1 |
| Week 2 | 15 | 2 | 22 |
| Week 4 | 29 | 23 | 36 |
| Week 6 | 43 | 37 | 50 |
| Week 8 | 57 | 51 | 64 |
| Week 10 | 71 | 65 | 78 |
| Week 12 | 85 | 79 | 99 |
| Week 16 | 113 | 100 | 127 |
| Week 20 | 141 | 128 | 155 |
| Week 24 | 169 | >155 | |

Table 4. Analysis Visit Windows for Non BK viruses

| Nominal Visit | Nominal Study Day | Visit Window Study Day | |
|----------------|-------------------|------------------------|-------------|
| | | Lower Limit | Upper Limit |
| Day 1/Baseline | 1 | 1 | 1 |
| Week 4 | 29 | 2 | 43 |
| Week 8 | 57 | 44 | 71 |
| Week 12 | 85 | 72 | 99 |
| Week 16 | 113 | 100 | 127 |

| | | | |
|---------|-----|------|-----|
| Week 20 | 141 | 128 | 155 |
| Week 24 | 169 | >155 | |

Table 5. Analysis Visit Windows for ECG data

| Nominal Visit | Nominal Study Day | Visit Window Study Day | |
|----------------|-------------------|------------------------|-------------|
| | | Lower Limit | Upper Limit |
| Day 1/Baseline | 1 | 1 | 1 |
| Week 2 | 15 | 2 | 92 |
| Week 24 | 169 | >92 | |

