3.1.2 Analysis Visits

Subject visits might not occur on protocol-specified days. Therefore, for the purpose of analysis, all scheduled, unscheduled, and early termination visits will be assigned to analysis visits according to the analysis windows ([Appendix 1](#)) based on study days. If there is more than 1 assessment in an analysis window, the assessment closest to the target day will be used in the analysis. If there are 2 assessments in a window equidistant from the target day, the later assessment will be used in the analysis.

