3.1.3 Definition of Baseline

Baseline is defined as the last non-missing measurement prior to the first dose of study treatment. This can be on Day 1 as long as the measurement is taken prior to the first dose. If a subject's day 1 samples are taken after the initial infusion, the samples taken prior to cycle 1 day 1, such as screening samples, may be used as the baseline values.

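### SAP Appendix B Table 5 files the post-infusion Day 1 ECG under a baseline label, so its change from the pre-dose baseline has no clear row

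*SAP*

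**What the plan says.** The schedule of activities (Protocol 1.3, repeated in SAP Appendix A) has ECGs at screening, Day 1, Week 2 and Week 24 or early termination. The Day 1 and Week 2 cells carry footnote 7: "Performed within 1 hour after study treatment administration and at the end of study or early termination visit". Footnote 1 sets the general rule for Day 1: "Unless noted otherwise, the Day 1 procedures must be performed within 96 hours of randomization and prior to study treatment administration". Footnote 7 is such an exception, so no pre-dose Day 1 ECG is scheduled.

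SAP 3.1.1 makes the day of the first dose Day 1. Under SAP 3.1.2, "all scheduled, unscheduled, and early termination visits will be assigned to analysis visits according to the analysis windows", and this is done by study day. When two assessments are equally close to the target day, "If there are 2 assessments in a window equidistant from the target day, the later assessment will be used in the analysis".

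SAP 3.1.3 states: "Baseline is defined as the last non-missing measurement prior to the first dose of study treatment". It admits a Day 1 value only if that value is pre-dose, and adds that where Day 1 samples were taken after the infusion, "the samples taken prior to cycle 1 day 1, such as screening samples, may be used as the baseline values".

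In Appendix B, "Table 5. Analysis Visit Windows for ECG data" has three rows. The first is "Day 1/Baseline | 1 | 1 | 1", the second (Week 2) runs from Day 2 to Day 92, and the third (Week 24) covers everything later. SAP 3.5.4 summarises observed ECG values and change from baseline, and lists all ECG parameters by patient.

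**The concern.** The row called baseline can receive only one scheduled ECG, and that ECG fails the SAP's own definition of baseline. The ECG that meets the definition has no row. Whoever programs the table must override either the label or the definition for the Day 1 record, and Table 5 does not say which.

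ECG change is a named component of the primary safety endpoint (SAP 2.3.1), Protocol 9.4.5 promises change from baseline for quantitative ECG parameters, and Protocol 2.4.2 lists arrhythmia among the possible effects of an infusion. The Day 1 ECG is the only scheduled one that captures the first infusion. At stake is whether its change from the pre-dose value appears in the change summary and, if the label is taken at face value, whether the later changes are measured from the wrong starting point.

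**Working it through.** No figure in the plan needs reproducing. The check places each scheduled ECG against the window table and the baseline definition.

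| Scheduled ECG | Study day | Relation to first dose | Table 5 row | Qualifies as baseline under 3.1.3 |
|---|---|---|---|---|
| Screening | -14 to -1 | Before | None | Yes |
| Day 1 | 1 | Within 1 hour after | First (Day 1 only) | No |
| Week 2 | 15 | After | Second (Day 2 to 92) | No |
| Week 24 | 169 | After | Third (after Day 92) | No |

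**Counts.** Each patient has 4 scheduled ECGs and Table 5 has 3 rows. Of the 4, 4 - 1 = 3 are post-dose, but only 2 rows come after the one labelled baseline. With about 60 patients at 20 per arm, up to 60 first-infusion ECGs fall in the row labelled baseline, 2 × 20 = 40 of them in the two PSL arms. The 60 screening ECGs fall in no row.

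**Reading 1: 3.1.3 is followed.** Let S be the screening ECG value, D the Day 1 post-infusion value and X the value at Week 2 or Week 24. Change is X - S, which is correct. The first-infusion change D - S can be calculated, but its record sits in a row called baseline, and nothing marks it as a post-baseline visit for the SAP 3.5.4 change summary.

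**Reading 2: the label is followed.** Change becomes X - D. Since (X - D) - (X - S) = -(D - S), each patient's Week 2 and Week 24 changes move by minus the first-infusion change. If d is the PSL-minus-placebo difference in mean D - S, the between-arm difference at both visits moves by -d. The documents give no value for d, so no size can be attached. Under Reading 1 the shift is zero.

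**Why ECG differs from the other tables.** All five Appendix B tables open with the same row. Footnote 17 has blood drawn before the infusion, and footnote 6 includes a vital-sign reading within 30 minutes before it. A qualifying Day 1 baseline therefore exists for those measures. For ECG none is scheduled.

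**The case against.** The strongest reply is that SAP 3.1.3 already settles the matter. Its first sentence is mandatory and speaks of a measurement, so it covers ECG and makes the screening tracing the baseline. The permissive wording about samples belongs to a later fallback sentence that is not needed here. The label looks like boilerplate shared by all five tables, none of which has a screening row, so the absence of one from Table 5 does not bar screening as baseline. Nor can the tie rule sensibly choose baselines: applied literally to vital signs, which are read before and several times after each infusion, it would select a post-infusion reading there too. It is more natural to read 3.1.2 as choosing visit records and 3.1.3 as choosing baseline. For ECG, the tie would also require an unscheduled pre-dose tracing on Day 1.

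All of this stands. A reader might infer that the ECG part of the primary safety analysis is biased, or that the trial has no valid ECG baseline. The documents do not support either inference: bias arises only if the row label is allowed to override an express definition. Nor is the first-infusion ECG lost from the report, because SAP 3.5.4 lists every ECG parameter and summarises observed values. The Week 2 ECG is also taken after an infusion, so with the 3.1.3 baseline one post-infusion change is tabulated in any case.

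The reply does not reach the row itself. With 3.1.3 followed exactly, Table 5 still places a post-dose ECG under a baseline label and gives it no post-baseline row.

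**Conclusion.** The conflict between Table 5 and SAP 3.1.3 is real but small. Under 3.1.3 the Week 2 and Week 24 changes are unbiased, and what is missing is a clear place for the change at the first infusion: 1 of 3 scheduled post-dose time points. A shift in the later changes is conditional on following the label over the definition, and its size is unknown.

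The effect is confined to a descriptive safety table. Protocol 9.4.2 calls the primary assessment qualitative and Protocol 9.1 plans no formal hypothesis testing. The conclusion assumes that sites follow footnote 7 and that the ECG falls on the same calendar day as the infusion. Severity is low.

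**What to change.** In SAP Appendix B Table 5, replace the first row with two rows:

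- *Baseline*: the last pre-dose ECG per 3.1.3, normally the screening one.
- *Day 1 post-infusion*: the ECG taken after the first infusion.

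Add a sentence that 3.1.3, and not the tie rule in 3.1.2, selects the ECG baseline. In SAP 3.5.4, include Day 1 post-infusion as a post-baseline visit in the change-from-baseline summary, so that the scheduled post-baseline time points go from 2 to 3.

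The cost is one split window row, one sentence and one extra row in the ECG summary. No new data are collected.
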